5.1 Background Information

SARS-CoV-2 / COVID-19: In December 2019, China notified the World Health Organization (WHO) of an outbreak of human respiratory illness in the city of Wuhan. The infecting agent is a novel coronavirus, called SARS-CoV-2 which causes atypical pneumonia (COVID-19). Cases have now been reported worldwide, and the WHO declared the outbreak a pandemic in March 2020 due to the levels of global spread and severity of the virus¹.

Previous novel coronaviruses include Middle East Respiratory Syndrome (MERS)-CoV, which emerged in 2012, and Severe Acute Respiratory Syndrome (SARS-CoV), which emerged in 2003. Both viruses are known to cause severe respiratory infections and are associated with a high case fatality rate.

Although the virus is presumed zoonotic in origin, person-to-person spread is evident with a median incubation period of 3 days (range 0 to 24 days), and the time from symptom onset to developing pneumonia is 4 days (range 2 to 7 days). Transmission occurs through respiratory droplets or direct contact, other means of transmission such as faecal-to-oral transmission have not been ruled out.² Symptoms of COVID-19 range from asymptomatic or mild to severe, and include fever, dry cough, and fatigue. The illness may evolve over the course of a week or longer, and in some cases progresses to acute respiratory distress syndrome and septic shock, requiring lengthy hospital stays.³

There are currently no approved antiviral treatments or vaccinations for human coronavirus infections, although Remdesivir (Gilead) has recently been issued an Emergency Use Authorization in the U.S. for those hospitalized with severe disease. Globally, scientists are working to develop COVID-19-based vaccines. Treatment for infected individuals is symptom-directed with supportive measures consisting of supplemental oxygen and conservative fluid administration. Compassionate use and trial protocols for several antiviral agents are underway.

Vaccine technology: The University of Queensland (UQ) has developed a candidate vaccine to provide protection against SARS-CoV-2 infection and COVID-19. This candidate, SARS-CoV-2 Sclamp, consists of the recombinant viral Spike glycoprotein (S) stabilized in its trimeric form, through the incorporation of the molecular clamp (MC) stabilization domain. This form is equivalent to that expressed on the virion surface and is thought to be the main target of a protective immune response. In order to create a suitable vaccine candidate, the SARS-CoV-2 S glycoprotein was further modified during screening to identify a form that could be produced as a soluble trimer.

The research team at UQ have previously demonstrated the value of the MC for producing candidate subunit vaccines for ten different viruses in preclinical studies. In January 2019, UQ received funding from the Coalition of Epidemic Preparedness Innovations (CEPI) and commenced work to establish and validate a 'Rapid Response Vaccine Pipeline' based on the molecular clamp platform for the purpose of producing vaccine candidates in the event of a novel virus epidemic. In January 2020 in response to increasing global concern about a potential public health emergency, CEPI requested UQ to redirect their studies to generate a candidate subunit

vaccine for COVID-19 and to assess safety and effectiveness of the candidate vaccine in animal models in anticipation of accelerating progress to a Phase 1 clinical study.

The SARS-CoV-2 Sclamp protein is produced by routine biopharmaceutical technologies which involve transfection of host Chinese Hamster Ovary (CHO) cells with plasmids encoding the modified gene for the clamped Spike protein. These cells are cultivated in suspension using protein free and animal component free media for production of the secreted recombinant protein. In order to facilitate rapid isolation of high purity material, the expressed protein is purified on an affinity column using a human monoclonal antibody directed against the molecular clamp domain. The material then undergoes additional downstream purification steps resulting in a high purity bulk protein which is aseptically dispensed into vials for clinical use. This protein is combined with adjuvant immediately prior to patient injection.

Further information regarding the vaccine technology can be found in the Investigator's Brochure.

Adjuvant: To stimulate a robust and appropriate immune response, the SARS-CoV-2-S-clamp subunit protein is administered with an adjuvant. The squalene-oil-in-water adjuvant MF59C.1 (Seqirus) has been selected due to its history of safe use in licenced vaccines for over 20 years with more than 100 million doses administered globally. An MF59C.1 adjuvanted influenza vaccine, FludaxTM is currently registered in Australia for use in persons aged 65 years and over for annual vaccination against influenza. Additionally, a H5N1 Pandemic vaccine, AflunovTM is registered for use in persons aged 18 years and older, for vaccination in the event of an influenza H5N1 pandemic being declared. Squalene-oil-in-water adjuvants have been well established to stimulate a balanced Th1/Th2 immune response that is expected to provide protection and mitigate the risk of any predisposition to enhanced disease via immunopathology. Studies have been designed and carried out using appropriate animal models, which further substantiate the safety and protective potential of SARS-CoV-2-Sclamp formulated with squalene-oil-in-water adjuvant MF59C.1 (Seqirus).

5.2 Rationale for Study Design

This will be a single centre, Phase 1, FIH, randomised, double-blind, placebo controlled, single and multiple ascending dose, 4-arm, parallel study.

The study will be conducted in two parts: Part 1 will include a young healthy adult population aged ≥ 18 - ≤ 55 years and Part 2 will include an older healthy adult population aged 56 years and over. Part 1 will be a single and multiple ascending dose, 4-arm, parallel study initiated before commencement of Part 2 so that safety can be assessed in the young adult population prior to exposure of the older adult population. Part 2 will be a multiple ascending dose, 3-arm, parallel study.

Since this is a FIH study with a novel vaccine antigen, a conservative approach to vaccine dosing will be adopted to ensure safety of study subjects. Sentinels will be used for cohorts 1, 2 and 3 such that two randomly selected subjects will receive either the first dose of SARS-CoV-2 Sclamp vaccine or placebo on Day 1 (and again on Day 29 for the second dose). After at least 24 hours from the time of administration of the first doses a review of the immediate post-vaccination safety data will be conducted by the Safety Review Committee (SRC) in accordance with the study

protocol. Should there be no safety concerns, the remaining subjects in the cohort will be dosed. The step-wise dose escalation study design is an additional precautionary measure, where the lower dose cohort will complete their first vaccination, and the cumulative safety data from the first 7 days will be evaluated by the SRC prior to initiating vaccination with sentinels of the intermediate dose of vaccine; same repeated at next (higher) dose level. After the first vaccination dose has been administered to Cohorts 1, 2 and 3 and the aggregated safety data reviewed, vaccination will be initiated for Cohorts 4, 5 and 6.

Subjects will be randomised into 1 of 4 treatment arms across 3 cohorts in Part 1 or into 1 of 3 treatment arms across 3 cohorts in Part 2, in a double-blinded manner. The double-blind will be maintained from first randomisation of an eligible subject until, at least, collection of data for all subjects is complete up to Day 57. After this day, the treatment assignment will be unblinded for all study team members, however subjects will remain blinded for the duration of the study.

Subjects will also have access to an electronic or paper diary to capture solicited and unsolicited AEs and will be instructed to advise the clinical site if they have been diagnosed with COVID-19, shown symptoms of COVID-19, or returned from overseas in the interim period. Where an acute respiratory illness, or any other relevant signs or symptoms that are clinically suspect for COVID-19, is identified and confirmed by nasal/oropharyngeal swab and SARS-CoV-2 specific PCR, subjects will be advised to contact the clinical site immediately. Subjects will be given an information sheet that defines the symptoms for COVID-19 at the time of receipt of their first study vaccination.

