5.4 Study Endpoints

Primary Safety Endpoints:

- Frequency, duration, and intensity of solicited local adverse events (AEs), including pain, redness, and induration for 7 days following each study treatment (for Days 1-3, Days 4-7 and Days 1-7).
- Frequency, duration, and intensity of solicited systemic adverse events (AEs), including fever, nausea, chills, diarrhoea, headache, fatigue, and myalgia for 7 days following each study treatment (for Days 1-3, Days 4-7 and Days 1-7).
- Frequency, duration, intensity, duration, and relatedness of unsolicited AEs through to Day 57. Frequency of Serious Adverse Events (SAEs), Medically-Attended Adverse Events (MAAEs), and any AEs leading to study withdrawal (including decision by the Principal

Investigator (PI) not to proceed with the second dose) at any time during study through to Day 394. Frequency and intensity of unsolicited AEs through to Days 57, 209, and 394

Primary Immunogenicity Endpoints:

- Geometric mean titre (GMT) of the serum antibody response to the Sclamp antigen compared to placebo by antigen specific ELISA at Day 29 (28 days after first dose) and Day 57 (28 days after second dose).
- GMT of the serum NAb titres to SARS-CoV-2 virus compared to placebo by MN assay at Day 29 (28 days after first dose) and Day 57 (28 days after second dose).

Secondary Immunogenicity Endpoints:

- Proportion of subjects with ≥ 4 fold increase in titre above baseline by ELISA at Days 15, 29, 43, 57, 209, and 394 post-first study treatment administration compared to placebo.
- Proportion of subjects with ≥ 4 fold increase in titre above baseline by MN assay at Days 15, 29, 43, 57, 209, and 394 post-first study treatment administration compared to placebo.
- GMT of the serum antibody response to the Sclamp antigen compared to placebo by antigen specific ELISA at Days 1, 15, 29 (28 days after first dose), and Days 43, 57 (28 days after second dose) and Days 209 and 394 (6 and 12 months post-second dose respectively).
- GMT of the serum NAb titres to SARS-CoV-2 virus compared to by MN assay at Days 1, 15, 29 (28 days after first dose), and Days 43, 57 (28 days after second dose) and Days 209, 394.

Exploratory Immunogenicity Endpoints:

- Proportion of subjects experiencing laboratory confirmed SARS-CoV-2 infection and/or severity graded COVID-19 disease between Days 57 and 394 compared to placebo.

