9.3 Randomisation and Blinding

Subjects will be administered either a cohort specific SARS-CoV-2 Sclamp vaccine or placebo (Treatment A, B, C, or D, see Section 9.5), according to the randomisation scheme produced by Syneos Health. Eligible subjects will be allocated a randomisation number associated with a randomised treatment prior to dosing, as close to dosing as feasible (Day 1) in order to minimise the number of subject withdrawals in the period between randomisation allocation and dosing.

The subjects and the clinical personnel involved in the collection, monitoring, revision, or evaluation of AEs, or personnel who could have an impact on the outcome of the study will be blinded with respect to the subject's treatment assignment (SARS-CoV-2 Sclamp vaccine or placebo). Except for circumstances related to subject safety (see Section 7.1), blinding will be maintained at least until data collection of all subjects in each cohort up to Day 57 i.e., when reporting and evaluation of all AEs have been completed up to 28 days post-second dose.

After data is collected for all subjects up to Day 57 the collected data will be locked and the treatment assignment will be unblinded to all study team members for the purpose of data analysis and generation of the Clinical Study Report (CSR) Part 1 and Addendum to the CSR Part 2. Subjects will remain blinded for the remaining duration of the study, thus the study will adopt a single-blind design after Day 57.

Designated pharmacy personnel at the clinical site not directly involved with the clinical aspects of the trial will prepare and dispense the study medication and will be aware of the randomisation code and the treatment.

In the event of an emergency for an individual subject in which knowledge of the study treatment is critical to the subject's medical management, or for the decision of dose escalation, the Investigator, or another attending study physician, will break the blind for that subject. An envelope for each subject containing their treatment assignment will be available from the pharmacy personnel. The Investigator, or other attending study physician, will make every effort to contact the Sponsor prior to unblinding a subject's treatment assignment and will record the date and reason for unblinding in the study source documents. In the event the Sponsor cannot be contacted prior to unblinding, the Sponsor will be contacted at the earliest feasible time after the unblinding has occurred.

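### The Day 57 unblinding covers all study team members, so site staff who assess primary safety endpoints to Day 394 lose their blind for a purpose (analysis and reporting) that does not need it

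*Protocol*

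**What the plan says.** **When the blind ends.** Section 5.2 keeps the double blind "until, at least, collection of data for all subjects is complete up to Day 57". Section 9.3 uses a different unit: "blinding will be maintained at least until data collection of all subjects in each cohort up to Day 57". Section 9.3 adds that the data are locked before unblinding.

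**Who is unblinded, and why.** Under Section 5.2, "the treatment assignment will be unblinded for all study team members, however subjects will remain blinded for the duration of the study". Section 9.3 gives the reason: "the treatment assignment will be unblinded to all study team members for the purpose of data analysis" and for writing the CSR (Part 1) and its addendum (Part 2). It then states the result: "Subjects will remain blinded for the remaining duration of the study, thus the study will adopt a single-blind design after Day 57".

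**Whose blinding the protocol treats as important.** Section 9.3 opens by blinding "The subjects and the clinical personnel involved in the collection, monitoring, revision, or evaluation of AEs", together with anyone else who could affect the outcome. Nothing keeps these site staff blinded after the Day 57 unblinding. The only later blinding described is that of the subjects (Sections 5.2 and 9.3) and of the serum laboratory staff (Section 11.2).

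**What is still being assessed.** In Section 5.4 the primary safety endpoints include SAEs, medically attended AEs (MAAEs) and AEs leading to withdrawal to Day 394, and "Frequency and intensity of unsolicited AEs through to Days 57, 209, and 394". An exploratory endpoint compares laboratory-confirmed infection and graded COVID-19 disease with placebo between Days 57 and 394.

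**The concern.** The unblinding is wider than its stated purpose. An unblinded analysis and report need statisticians, programmers, medical writers and some sponsor staff. They do not need the people at the site who question subjects about events and grade them. Section 9.3 recognises that AE evaluators should be blinded, then ends that protection on the ground that AE evaluation is complete to 28 days after the second dose. The primary safety endpoints do not end there.

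Some of the later assessments involve judgement. Section 9.15.2 has staff evaluate seriousness and severity. Section 9.10.6.7 makes symptom-driven SARS-CoV-2 testing optional up to Day 394. Section 9.15.2.2 has study personnel apply the Appendix I checklist when a suspected case has no laboratory result. An assessor who knows the arm may probe, grade or test differently.

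The primary safety objective in Section 5.3 is a comparison with placebo, and the placebo groups are small, so a few altered classifications would be visible in the tables.

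**Working it through.** **Inputs**

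- Dose days 1 and 29; Day 57 is 28 days and Day 394 is 12 months after the second dose (Sections 5.3 and 9.2).
- Visit window of ±2 days at Day 57 (Section 4).
- AE follow-up visits on Days 8, 15, 36, 43, 57, 209 and 394 (Synopsis, Safety Measurements).
- Cohort 1 expected to start in July 2020; Cohort 6 expected to complete Day 57 in December 2020 (Synopsis, Expected Start and End Dates).
- 8 placebo subjects in each of 6 cohorts (Sections 6 and 8.2).

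**Step 1: reproduce the plan's days.** 29 + 28 = 57 and 29 + 365 = 394. Both match.

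**Step 2: share of post-dose follow-up open to unblinded assessors.** With unblinding on a subject's study day u, share = (394 − u) / (394 − 1).

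| Case | u | Calculation | Open share |
|---|---|---|---|
| Upper bound: unblinded at the subject's own Day 57 | 57 | 337/393 | 85.8% |
| End of the Day 57 window | 59 | 335/393 | 85.2% |
| Cohort 1 dosed 31 July, unblinded 1 December 2020 | 124 | 270/393 | 68.7% |
| 1 July to 1 December, or 31 July to 31 December 2020 | 154 | 240/393 | 61.1% |
| 1 July to 31 December 2020 | 184 | 210/393 | 53.4% |

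The last three rows take the Section 5.2 trigger to mean all subjects in all cohorts. The exact days within July and December are my assumption, because the protocol gives only the months. The share would fall to half only at u = 394 − 393/2 = 197.5.

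**Step 3: the exploratory infection window.** Days 57 to 394 span 337 days. With unblinding at Day 124 to 184, the part still blinded for a Cohort 1 subject is (124 − 57)/337 = 67/337 = 20% up to (184 − 57)/337 = 127/337 = 38%. The window is therefore wholly unblinded only at the upper bound.

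**Step 4: count visits instead of days.** Of the seven AE follow-up visits, only Days 209 and 394 come after Day 57: 2 of 7.

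**Step 5: sort the assessments against Day 57.**

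- Complete by Day 57: solicited AEs (7 days after each dose), vital signs and ECG (last at Day 30), scheduled safety laboratory tests and urinalysis (last at Day 57), relatedness and duration of unsolicited AEs as endpoint components, and the primary immunogenicity samples (Days 29 and 57).
- Continuing to Day 394: SAEs, MAAEs, AEs leading to withdrawal, frequency and intensity of unsolicited AEs, discretionary SARS-CoV-2 testing and the COVID-19 checklist.

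**Step 6: sensitivity to one reclassified subject.** In one cohort's placebo group, 1/8 = 12.5 percentage points. In all placebo subjects pooled, 1/48 = 2.1 percentage points.

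**The case against.** The strongest reply is that this is a disclosed choice in a Phase 1 trial with modest consequences. The protocol itself labels the later period single-blind. It has no power calculation (Section 8.2), no inferential safety analysis (Section 11) and no success rule (Section 11.3), and the infection endpoint is exploratory. Much of the late ascertainment also depends little on the assessor. An MAAE is defined by an unscheduled medical appointment, which a blinded subject would usually initiate. SAEs follow set criteria, and a COVID-19 infection is an SAE by rule. Infection is laboratory confirmed, and symptom prompts go to blinded subjects, who may turn to their own practitioner.

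Most of this stands, and it limits the size of the point. It does not remove the mismatch between purpose and scope. Descriptive comparisons with placebo can still be affected by knowledge of the arm, and Section 11.3 bases dose selection on the joint safety and immunogenicity profile. Intensity grading, discretionary testing and the clinical checklist remain matters of judgement.

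Three stronger readings are tempting, and the documents do not support them:

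- A reader might infer that most safety assessment is unblinded. That is true of calendar time only. The bulk of planned assessments, and 5 of 7 AE follow-up visits, fall at or before Day 57.
- A reader might take 86% of follow-up, and all of the infection window, as what will happen. Both are upper bounds, because unblinding waits for other subjects' Day 57 data and a lock.
- A reader might list relatedness among the exposed primary endpoints. Section 5.4 stops it at Day 57. Relationship is still recorded for later AEs (Section 9.15.2), but not as a primary endpoint component.

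**Conclusion.** The point holds in a limited form. The protocol unblinds everyone for a task that needs only the analysis and reporting staff, and by doing so removes the blind from site assessors while primary safety endpoints continue to Day 394.

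By time, the exposure is at most 337 of 393 post-dose days (86%). It is about 53% to 69% for a Cohort 1 subject on the most favourable reading of the trigger, given the assumed July and December 2020 dates. The possible bias is confined to classification of SAEs, MAAEs and withdrawal AEs, intensity of unsolicited AEs, and site-level COVID-19 testing and case finding. Its size cannot be calculated from the protocol, and it would be wrong to say that late differences between arms are uninterpretable.

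The trigger wording is a related defect. Section 5.2 waits for all subjects and Section 9.3 for all subjects in each cohort, while Sections 11 and 12 plan an unblinded Part 1 report once Part 1 has reached Day 57. These give different unblinding dates for the same subject. The correction is cheap and worth making; the point does not undermine the Day 57 analyses.

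**What to change.** In Sections 5.2 and 9.3:

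1. Limit unblinding after the Day 57 lock to the statisticians, programmers, medical writers and sponsor staff needed for the CSR and its addendum, identified by role.
2. Withhold individual treatment assignments, including subject-level listings, from site staff who assess AEs or COVID-19 until the Day 394 lock.
3. Leave emergency unblinding unchanged.
4. State one trigger (by cohort, by part or for the whole study) in both sections, consistent with the reporting plan in Sections 11 and 12.

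If the sponsor keeps the full unblinding, the endpoints and reports should label safety and COVID-19 results after unblinding as single-blind and say from which date that applies to each cohort.

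The cost is protocol wording plus access control on the listings and the randomisation file for about 11 more months (337 days from Day 57 to Day 394). Sample size, visits and analyses do not change.

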5.2.1 Analytes to be Measured

Analysis of the humoral response for COVID-19 will include an ELISA for the SARS-CoV-2 Sclamp antigen specific immune response, analysis of domain specificity and immunoglobulin isotype induction via Luminex Assay, analysis of microneutralisation (MN) assessed via SARS-CoV-2 virus, and ADCC that will include assessment of potential correlates of protection.

The induction of antigen specific T-cells will be assessed through the stimulation of peripheral blood mononuclear cells (PBMCs) with a vaccine specific peptide library and analysed by multi-colour flow cytometry following surface staining for CD3, CD4, CD8, and intracellular cytokine staining for IFN- γ , TNF- α , IL-2, IL-4, IL-13, IL-17a, CD107a, and Granzyme B.

5.2.2 Choice of the Dose

The planned SARS-CoV-2 Sclamp doses to be investigated in this FIH study are 5, 15, and 45 mcg. The study is designed as a dose escalation study with the safety of the 5 mcg dose to be evaluated by a Safety Review Committee prior to escalation to the 15 mcg, and similarly prior to escalation to the 45 mcg dose.

The starting dose of 5 mcg and highest dose of 45 mcg SARS-CoV-2 Sclamp are based on comparable viral subunit vaccines approved for use as outlined below and in the IB:

RECOMBIVAX HB[®] (Hepatitis B vaccine, recombinant, Adjuvanted)

- Paediatric and adolescent formulation: Contains 5 mcg antigen + 0.25mg aluminium (provided as amorphous aluminium hydroxyphosphate) – Recommended 3 doses of 0.5 mL given by IM injection on a 0-, 1-, and 6-month schedule.
- Adult (≥ 20 years) formulation: Contains 10 mcg antigen + 0.5mg aluminium (provided as amorphous aluminium hydroxyphosphate) - Recommended 3 doses of 0.5 mL given by IM injection on a 0-, 1-, and 6-month schedule.
- HEPLISAV-B[®] (Hepatitis B vaccine, recombinant, Adjuvanted)
 - Adult (≥ 18 years): Contains 20 mcg antigen + 3mg CPG-1018 - Recommended 2 doses of 0.5 mL given by IM injection on a 0- and 1-month schedule.
- GARDASIL^{®9} (Human Papillomavirus 9-valent vaccine, recombinant, Adjuvanted)
 - Children (>9 years) and adult: Contains 20 - 60 mcg antigen per strain for each of nine strains + 0.5mg aluminium (provided as amorphous aluminium hydroxyphosphate) – Recommended 3 doses of 0.5 mL given by IM injection on a 0-, 2-, and 6-month schedule.
- SHINGRIX[®] (Zoster Vaccine Recombinant, Adjuvanted),
 - Adult (>50 years): Reconstituted vaccine contains 50 mcg antigen + AS01b adjuvant – Recommended 2 doses of 0.5 mL given by IM injection on a 0-, 2-, and 6-month schedule.

Additionally, the choice of dose is supported by previous experience evaluating MC vaccines. Immunopathology and animal protection of SARS-CoV-2 Sclamp have investigated doses of 5 mcg per dose in mice indicating that a neutralising immune response was induced by the SARS-CoV-2 Sclamp vaccine. Further pre-clinical examinations in hamsters (also at 5 mcg per dose) and ferrets (at 20 mcg per dose), are ongoing, the results of which will be included in the SARS-CoV-2 Sclamp Investigator's Brochure.

Objectives and Endpoints

